### 5.3. Screening/Baseline/Run-in Failures

Screen failures are defined as subjects who consent to participate in the clinical trial but are never subsequently randomized. In order to ensure transparent reporting of screen failure subjects, meet the Consolidated Standards of Reporting Trials (CONSORT) publishing requirements, and respond to queries from Regulatory authorities, a minimal set of screen failure information is required including Demography, Screen Failure details, Eligibility Criteria, and Serious Adverse Events (see Section 7.3.1.5).

Subjects who do not qualify to participate in the study due to a screening laboratory value or ECG abnormality can repeat the test once within the original screening window, if the Investigator believes there is a reasonable possibility that the subject would be eligible if re-tested.

Subjects can be re-screened only on approval of the GSK Medical Monitor and only once. Re-screening is allowed when a subject failed inclusion/exclusion criteria or some other screening condition initially, but the Investigator believes there is a reasonable probability that the subject would be eligible if re-screened.

### 5.4. Withdrawal/Stopping Criteria

Subjects may be withdrawn from the study for any of the following reasons:

- A subject may withdraw from study treatment at any time at his/her own request, or may be withdrawn at any time at the discretion of the Investigator for safety, behavioural or administrative reasons. If a subject withdraws from the study, he/she may request destruction of any samples taken, and the Investigator must document this in the site study records. The reason for withdrawal should be documented in the Case Report Form (CRF).

- The Sponsor's request, for reasons such as significant protocol deviations or subject safety concern (and after discussion with the Investigator).
- If a subject is withdrawn from study treatment, this subject is also considered to be withdrawn from the study.
- Study is terminated by the Sponsor.

If a subject is withdrawn, the Sponsor may decide to replace that subject and this will be done through the Interactive Response Technology System (IRTS).

If a subject chooses to withdraw from the study after dosing then the Investigator must make every effort to complete the follow-up assessments detailed in the Time and Events Table (Section 7.1).

The following actions must be taken in relation to a subject who fails to attend the clinic for a required study visit:

- The site must attempt to contact the subject and re-schedule the missed visit as soon as possible.
- The site must counsel the subject on the importance of maintaining the assigned visit schedule and ascertain whether or not the subject wishes to and/or should continue in the study.
- In cases where the subject is deemed 'lost to follow up', the Investigator or designee must make every effort to regain contact with the subject (where possible, 3 telephone calls and if necessary a certified letter to the subject's last known mailing address or local equivalent methods). These contact attempts should be documented in the subject's medical record.
- Should the subject continue to be unreachable, only then will he/she be considered to have withdrawn from the study with a primary reason of "Lost to Follow-up".

#### **5.4.1. Individual Safety Stopping Criteria**

Study medication will be discontinued in the event of any of the following:

- If a subject experiences a serious or severe clinically significant AE that in the clinical judgement of the Investigator, after consultation with the medical monitor, is possibly, probably or definitely related to investigational product.
- The subject becomes pregnant.
- The subject initiates treatment with any prohibited medications for the treatment of RA as listed in Section 6.11.2.
- The subject develops a serious opportunistic or atypical infection.
- If any of the liver chemistry stopping criteria (Section 5.4.3), QTc stopping criteria (Section 5.4.4), or Haematologic stopping criteria (Section 5.4.5) are met.
- The subject experiences any signs of suicidal ideation or behaviour (Section 7.3.7).

## 5.4.2. Group Safety Stopping Criteria

[figure not shown]
In addition to the criteria specified above, AEs, SAEs, laboratory abnormalities, ECG abnormalities and changes in vital signs occurring across all randomised subjects will be regularly reviewed by the Sponsor Safety Review Team (SRT) in order to ensure appropriate subject safety. Any changes to the study due to safety reasons will be promptly communicated to the appropriate Regulatory Authorities.

## 5.4.3. Liver Chemistry Stopping Criteria

**Liver chemistry stopping and increased monitoring criteria** have been designed to assure subject safety and evaluate liver event etiology (in alignment with the FDA premarketing clinical liver safety guidance).

<http://www.fda.gov/downloads/Drugs/GuidanceComplianceRegulatoryInformation/Guidances/UCM174090.pdf>

**Figure 3 Phase II Liver Chemistry Stopping Criteria – Liver Stopping Events Algorithm**

Liver Safety Required Actions and Follow up Assessments Section can be found in [Appendix 2](#).

### 5.4.3.1. Study Treatment Restart or Rechallenge

Study treatment restart or rechallenge after liver chemistry stopping criteria are met by any subject participating in this study is not allowed.

#### 5.4.4. QTc Stopping Criteria

A subject who meets either of the bulleted criteria below will be withdrawn from the study:

- QTc >500 msec or Uncorrected QT >600 msec
- Change from baseline of QTc >60 msec

For patients with underlying **bundle branch block**, follow the discontinuation criteria listed below:

Baseline QTc with Bundle Branch Block	Discontinuation QTc with Bundle Branch Block
<450 msec	>500 msec
450–480 msec	≥530 msec

- The *same* QT correction formula *must* be used for *each individual subject* to determine eligibility for and discontinuation from the study. This formula may not be changed or substituted once the subject has been enrolled.

For example, if a subject is eligible for the protocol based on QTcB, then QTcB must be used for discontinuation of this individual subject as well.

- Once the QT correction formula has been chosen for a subject's eligibility, the *same formula* must continue to be used for that subject *for all QTc data being collected for data analysis*. Safety ECGs and other non-protocol specified ECGs are an exception.
- The decision to withdraw a subject will be based on an average QTc value of triplicate ECGs. If an ECG demonstrates a prolonged QTc, obtain 2 more ECGs over a brief period (5-10 minutes), and then use the averaged QTc values of the 3 ECGs to determine whether the subject should be discontinued from the study.

#### 5.4.5. Haematologic Stopping Criteria

Study treatment will be stopped for a subject if any of the following haematological stopping criteria is met:

- Haemoglobin - an absolute decrease of  $\geq 2$  g/dL from baseline (pre-dose Day 1)
- Platelets  $< 50 \times 10^9/L$

#### 5.5. Subject and Study Completion

A completed subject is one who has completed all phases of the study including the follow-up visit.

The end of the study is defined as the last subject's last visit.

## 6. STUDY TREATMENT

### 6.1. Investigational Product and Other Study Treatment

The term ‘study treatment’ is used throughout the protocol to describe any combination of products received by the subject as per the protocol design. Study treatment may therefore refer to the individual study treatments or the combination of those study treatments.

	Study Treatment	
Product name:	GSK2982772	Placebo
Dosage form:	Tablet	Tablet
Unit dose strength(s)/Dosage level(s):	30 mg	NA
Route of Administration	For oral use only	For oral use only
Dosing instructions (with amendment 03):	Take TWO tablets three times a day as directed by your physician	Take TWO tablets three times a day as directed by your physician
Dosing instructions (prior to amendment 03):	Take TWO tablets in the MORNING and TWO tablets in the EVENING as directed	Take TWO tablets in the MORNING and TWO tablets in the EVENING as directed
Physical description:	White to almost white, round, film coated tablet	White to almost white, round, film coated tablet
Source of procurement	Study medication is supplied by GlaxoSmithKline	Placebo is supplied by GlaxoSmithKline

### 6.2. Treatment Assignment

At Screening a unique Subject Number will be assigned to any subject who has signed a consent form. The unique Subject Number will be used to identify individual subjects during the course of the study. Any subject that is re-screened outside of the allowed screening window at the approval of the GSK Medical Monitor, must be assigned a new unique Subject Number.

Subjects who meet screening eligibility criteria will be randomised to a treatment group through an Interactive Response Technology System (IRTS). The IRTS will confirm the subject’s CRF number (Subject Number) and provide the randomisation number, where:

- A randomisation number will be assigned from a randomisation schedule generated by Clinical Statistics, prior to the start of the study, using validated internal software. Once assigned, this number must not be reassigned to any other subject in the study.

Therefore, the randomisation is centrally controlled by the IRTS.

Subjects will be randomised to receive either GSK2982772 or placebo in a 2:1 ratio.

### 6.3. Planned Dose Adjustments

No dose adjustments are allowed.

### 6.4. Blinding

This will be a double blind (sponsor unblinded) study and the following will apply:

- Sponsor unblinded refers only to the Data Review Committee, consisting of the GSK Project Physician Lead (PPL), study statistician, study pharmacokineticist, Pattern Recognition Receptor (PRR) Discovery Performance Unit (DPU) Head, Early Development Lead (EDL) and Safety Review Team (SRT) Leader, or their designees on an ongoing basis. A physician external to the GSK2982772 project team may also be involved in the data review. A data review charter will identify the specific GSK individuals involved; outline in detail the activities of this review, and how the integrity of the study will be maintained. The rest of the core GSK study team will remain blinded.
- The Investigator or treating physician may unblind a subject's treatment assignment **only in the case of an emergency** OR in the event of a serious medical condition when knowledge of the study treatment is essential for the appropriate clinical management or welfare of the subject as judged by the Investigator. Investigators have direct access to the subject's individual study treatment.
- It is preferred (but not required) that the Investigator first contacts the Medical Monitor or appropriate GSK study personnel to discuss options **before** unblinding the subject's treatment assignment.
- If GSK personnel are not contacted before the unblinding, the Investigator must notify GSK as soon as possible after unblinding, but without revealing the treatment assignment of the unblinded subject to his/her study staff or GSK, unless that information is important for the safety of subjects currently in the study.
- The date and reason for the unblinding must be fully documented in the CRF.
- A subject will be withdrawn if the subject's treatment code is unblinded by the Investigator or treating physician. The primary reason for discontinuation (the event or condition which led to the unblinding) will be recorded in the CRF.
- GSK's Global Clinical Safety and Pharmacovigilance (GCSP) staff may unblind the treatment assignment for any subject with an SAE. If the SAE requires that an expedited regulatory report be sent to one or more regulatory agencies, a copy of the report, identifying the subject's treatment assignment, may be sent to Investigators in accordance with local regulations and/or GSK policy.

## **6.5. Packaging and Labeling**

The contents of the label will be in accordance with all applicable regulatory requirements.

## **6.6. Preparation/Handling/Storage/Accountability**

No special preparation of study treatment is required.

- Only subjects enrolled in the study may receive study treatment and only authorized site staff may supply or administer study treatment. All study treatments must be stored in a secure environmentally controlled and monitored (manual or automated) area in accordance with the labelled storage conditions with access limited to the Investigator and authorized site staff.
- The Investigator, institution, or the head of the medical institution (where applicable) is responsible for study treatment accountability, reconciliation, and record maintenance (i.e. receipt, reconciliation and final disposition records).
- Further guidance and information for final disposition of unused study treatment are provided in the SRM.
- Under normal conditions of handling and administration, study treatment is not expected to pose significant safety risks to site staff.
- A Material Safety Data Sheet (MSDS)/equivalent document describing occupational hazards and recommended handling precautions either will be provided to the Investigator, where this is required by local laws, or is available upon request from GSK.

## **6.7. Compliance with Study Treatment Administration**

When subjects are dosed at the site, they will receive study treatment directly from the Investigator or designee, under medical supervision. The date and time of each dose administered in the clinic will be recorded in the source documents. The dose of study treatment and study subject identification will be confirmed at the time of dosing.

When subjects self-administer study treatment(s) at home, compliance with GSK2982772 and placebo will be assessed and documented through the review of the subject's diary card and querying the subject during the site visits. A record of the number of GSK2982772 or placebo tablets dispensed to and taken by each subject must be maintained and reconciled with study treatment and compliance records. Treatment start and stop dates, including dates for treatment delays and/or dose reductions will also be recorded in the CRF.

Subjects will be given instructions on compliance and treatment with MTX (if applicable). The date, time and total weekly dose will be recorded in the study diary cards and the CRF.

## **6.8. Treatment of Study Treatment Overdose**

For this study, any dose of GSK2982772 >180 mg daily will be considered an overdose. GSK does not recommend specific treatment for an overdose. The Investigator will use clinical judgement to treat any overdose as and when they are made aware of this.

In the event of an overdose, the Investigator or treating physician should:

1. Contact the Medical Monitor immediately.
2. Closely monitor the subject for adverse events (AEs)/serious adverse events (SAEs) for at least 48 hours following the last dose of GSK2982772.
3. Obtain a plasma sample for pharmacokinetic (PK) analysis if requested by the Medical Monitor (determined on a case-by-case basis).
4. Document all details of the overdose in the CRF.

Decisions regarding dose interruptions or modifications will be made by the Investigator in consultation with the Medical Monitor based on the clinical evaluation of the subject.

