#### **4.2.2. Treatment Period**

Subjects will be randomly assigned to either GSK2982772 60 mg or placebo orally three times daily (approximately 8 hours apart) for 84 days (12 weeks). Subjects that were randomised prior to protocol amendment 03 being approved in each country were randomly assigned to either GSK2982772 60 mg or placebo orally two times daily (approximately 12 hours apart) for 84 days (12 weeks).

Further guidance and information for study treatment and dosing are provided in the Study Reference Manual (SRM).

During the 84 day (12 week) treatment period, subjects will attend the clinical site for visits on Days 1, 8, 15, 29, 43, 57, 71 and 85. At specific visits, subjects must not take study treatment prior to their scheduled visit (see Section 7.1). On Days 22, 36, 50, 64 and 78, each subject will be contacted by telephone and asked about their general health, study medication compliance and diary card completion. Subjects will be given a diary card at each of the visits on which they will be instructed to record their daily study medication and concomitant medication taken and any adverse events.

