### **4.3. Type and Number of Subjects**

A sufficient number of subjects will be screened so that approximately 24 subjects with moderate to severe RA are randomised into the study on a TID regimen. Prior to protocol amendment 3 being approved in each country, no more than 18 subjects will be randomised into the study on a BID regimen. Should the overall drop-out rate be higher than anticipated, additional or replacement subjects may be randomised (up to an overall maximum of 48) into the study at the discretion of the Sponsor.

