**Footnotes:**

1. Full medical history (includes past and current conditions, medication history, substance usage, and family history of premature CV disease).
2. Full physical exam (includes height/weight at screening, height not measured at later time points).
3. Triplicate ECG to be performed at screening only.
4. Pre-dose.
5. Any SAEs assessed as related to study participation (e.g., protocol-mandated procedures, invasive tests, or change in existing therapy) or related to a GSK product will be recorded from the time a subject consents to participate in the study up to and including any follow-up. AEs will be collected from the start of Study Treatment until the follow-up contact. On Days 22, 36, 50, 64, and 78, subjects will be questioned about their general health status via phone call.
6. All PRO assessments should be conducted on site before any tests, procedures, or assessments, to avoid influencing the subjects' perception.
7. DCE-MRI will be performed on all subjects, provided that sites have DCE-MRI capability and experience (e.g., hardware and software requirements). If sites do not have DCE-MRI capability or experience, a regular MRI will be performed of the affected hand/wrist. If the same joint is used for MRI and synovial biopsy, MRI should be performed before biopsy (if applicable).
8. Subjects must take study medication three times a day approximately 8 hours apart. Exact time of dosing to be recorded in diary cards. On Day 1, the first study dose will be administered at the site. On Days 8, 43 and 85 only, subjects must not take their medication at home in the morning. Subjects will complete pre-dose assessments and then will be administered their morning dose of medication at site on Days 8 and 43. On Day 85, subjects are no longer receiving study medication.
9. If urine pregnancy test is positive, a confirmatory serum pregnancy test must be performed.
10. Haematology and chemistry only. No urinalysis required on Days 29, 57 and 71. When clinical laboratory samples are taken on the same day as the MRI, the samples should be taken first prior to the administration of the contrast fluid with MRI. If this is not feasible (i.e. MRI is performed first), it is recommended that a separate IV catheter or straight venipuncture be performed in the *opposite* arm to where the MRI contrast fluid was administered.

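### The Time and Events Table tells every subject to dose three times a day although the protocol keeps a twice-daily cohort, and the single overdose limit would not flag the result (150% of the assigned dose).

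*Protocol*

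**What the plan says.** The Amendment 03 text describes two regimens.

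- **Twice daily (BID).** Section 4.2.2 says that subjects randomised before Amendment 03 was approved in their country "were randomly assigned to either GSK2982772 60 mg or placebo orally two times daily (approximately 12 hours apart) for 84 days (12 weeks"). Section 6.1 keeps their label instruction: "Take TWO tablets in the MORNING and TWO tablets in the EVENING as directed". Section 4.3 caps the cohort: "no more than 18 subjects will be randomised into the study on a BID regimen".
- **Three times daily (TID).** Section 6.1 gives the instruction under Amendment 03: "Take TWO tablets three times a day as directed by your physician".

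Section 6.3 states: "No dose adjustments are allowed". No section provides for BID subjects to move to TID.

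Two rules carry only the TID figures. Footnote 8 of the Time and Events Table (Section 7.1) reads "Subjects must take study medication three times a day approximately 8 hours apart", and the study-medication row of the table carries the same frequency. Section 7 makes adherence to that table mandatory. Section 6.8 reads: "For this study, any dose of GSK2982772 >180 mg daily will be considered an overdose". Section 6.8 of the Amendment 04 text repeats this limit unchanged.

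**The concern.** For a BID subject, footnote 8 and the table row conflict with Sections 4.2.2 and 6.1. The footnote makes no exception for subjects randomised earlier, and the statement of where Amendment 03 applies makes none for subjects already on treatment. A site working from the table alone would give such a subject a third daily dose that was never assigned.

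Section 6.8 would not pick this up, because its limit sits exactly at the full TID daily dose. The steps that would not start are immediate contact with the Medical Monitor, close monitoring for at least 48 hours, a PK sample if requested, and the overdose entry in the CRF.

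There is also a possible effect on the analysis. Under Section 9.3.1, if 12 or more subjects are randomised to BID, the treatment groups for active drug are separated by dosing frequency. A BID subject who in fact took three doses a day would blur that separation.

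**Working it through.** **Inputs**

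- Tablet strength 30 mg, two tablets per dose (Section 6.1).
- Doses per day: 2 for BID, 3 for TID (Sections 4.2.2 and 6.1).
- Overdose limit: strictly more than 180 mg daily (Section 6.8).
- BID cohort: at most 18 subjects (Section 4.3), randomised 2:1 (Section 6.2).

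**Reproducing the plan's figures**

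Daily dose = tablets per dose × 30 mg × doses per day.

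- TID: 2 × 30 × 3 = 180 mg. This equals the Section 6.8 limit.
- BID: 2 × 30 × 2 = 120 mg.
- Active BID subjects at the cap: 18 × 2/3 = 12, which agrees with the maximum given in Section 9.2.1.

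**Applying the limit to each regimen**

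| Tablets in a day | mg | % of BID dose | % of TID dose | Above 180 mg? |
|---|---|---|---|---|
| 4 | 120 | 100 | 67 | no |
| 5 | 150 | 125 | 83 | no |
| 6 | 180 | 150 | 100 | no |
| 7 | 210 | 175 | 117 | yes |

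Because the inequality is strict, a BID subject can reach 180/120 = 150% of the assigned dose without meeting it. The first whole-tablet total that counts is 7 tablets, which is 175% of the BID dose but 117% of the TID dose.

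**Combining the two rules**

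A BID subject who obeys footnote 8 takes 6 tablets, 180 mg: exactly the largest amount that Section 6.8 does not flag.

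**Who could be exposed**

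Only BID subjects on active drug who are still within their 84 days when Amendment 03 takes effect in their country. The protocol does not give that number. It is at least 0 and at most about 12. Overlap is plausible: Section 4.3 speaks of BID randomisation in the future tense, and Table 4 still gives the BID cohort as a range (7 to 12, or 12 to 18), so enrolment was not treated as final when the text was written.

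**The case against.** The strongest reply is that Section 6.8, read alone, contradicts nothing. It does not tell anyone to take 180 mg, and a single study-wide limit at the highest assigned daily dose is a permissible choice. That stands. The contradiction lies in the Time and Events Table; Section 6.8 matters because it would not catch the consequence.

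A second reply is that extra dosing would be seen anyway. This largely stands too. Dose times go into diary cards, diaries are reviewed and tablets reconciled (Section 6.7), the telephone calls ask about compliance (Section 4.2.2), and adverse events are collected whether or not an overdose is declared (Section 7.3.1.1). What would be lost is the set of prompt Section 6.8 actions.

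Third, a site would have to put one footnote above Sections 4.2.2, 6.1 and 6.3, and the Study Reference Manual, which is not available here, may give clearer dosing guidance. This lowers the likelihood. It does not remove the conflict, because Section 7 makes the table binding.

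A reader might also infer that adverse events would be counted wrongly against a primary objective defined by regimen. The documents do not support this. The primary objective in Section 3 names only the TID regimen, and with fewer than 12 BID subjects Section 9.3.1 ignores dosing frequency. An overdose flag would not in itself change the group in which an event is counted.

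**Conclusion.** The point holds as an internal inconsistency in an operative dosing instruction. For a BID subject on treatment under Amendment 03, the Time and Events Table and Sections 4.2.2 and 6.1 cannot both be followed. Following the table gives 180 mg/day, 150% of the assigned 120 mg, and does not trigger Section 6.8.

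The practical reach is small: 0 to about 12 subjects on active drug, in a cohort that closes as each country adopts the amendment. The conclusion assumes that BID subjects stay on BID to the end of their 84 days, as Section 4.2.2 describes, and that some of them are still on treatment at the changeover. The possible effect on the comparison by dosing frequency arises only if 12 or more subjects are randomised to BID.

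Two stronger readings should be set aside. One is that 180 mg/day is unsafe. Nothing here shows that: it is the assigned dose of the TID group, and Section 4.5 describes an earlier study with repeat doses up to 120 mg BID (240 mg/day). The other is that all 18 possible BID subjects are affected. That figure is the enrolment cap and includes placebo subjects and any who finished treatment before the changeover.

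The Amendment 04 text available ends before its Time and Events Table, so only the repetition of the Section 6.8 limit could be confirmed there.

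**What to change.** Reconcile the study-medication row and footnote 8 of the Time and Events Table with Sections 4.2.2 and 6.1, so that the table states which subjects its dosing frequency applies to. Ask the sponsor to confirm whether the limit in Section 6.8, in both the Amendment 03 and the Amendment 04 text, is intended for both regimens, and to say so there. No dose or limit is proposed here; those decisions belong to the sponsor.

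The cost is a few words in the table, its footnote and Section 6.8, in an amendment. No change to the design, the sample size or the analysis is needed.
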